For a power calculation to determine the sample size, historical data was utilized from prior clinical study that examined the effect of bronchodilator (B2-agonist) treatment on the improvement of the peak flow measurement after 30 minutes of the initial bronchodilator treatment⁴. In this study, the mean PEFR improved from 27% to 39% at 30 minutes after the initial bronchodilator treatment. We hypothesize that mean PEFR of the intervention group at 30 minutes of the bronchodilator therapy will be at least 10 points higher than the control group (i.e. mean PEFR \geq 49% at 30 minutes of the initial bronchodilator therapy). Group sample sizes of 34 and 34 is required to achieve a power $> 80\%$ to reject the null hypothesis of equal means when the groups mean difference is 10.0 with a standard deviation for both groups of 14.4 and with a significance level (alpha) of 0.050 using a two-sided two-sample equal-variance t-test.

Taking into consideration the screen failures the disqualification and drop-outs, we are anticipating enrolling around 110 patients in order to have 68 patients who will complete the study objectives.

For the statistical analysis treatment evaluations will be performed on the principle of intention to treat (ITT) using the data collected from all randomized participants who completed the study procedures including the two parts of the informed consent form (ICF). Demographics and baseline characteristics of patients will be summarized for each group. Continuous variables will be reported as mean \pm standard deviation, with minimum, median, and maximum values.

Categorical variables will be reported as n and %. All statistical testing will be two-sided with alpha=0.05.

For the primary outcome, mean PEFR at 30 minutes post-bronchodilator treatment, analysis of covariance (ANCOVA) with adjustment for baseline PEFR will be utilized.

ANCOVAs with adjustment for baseline values, and incorporating repeated measures where appropriate, will be utilized for the following secondary outcomes: absolute value of PEFR (L/Min) at 30 minutes, PEFR percentage of predicted at 60 minutes and 180 minutes, FEV1 percentage of predicted as well as absolute FEV1 (L/Sec) at 30 minutes, 60 minutes and 180 minutes, Borg dyspnea score at 30 minutes, 60 minutes and 180 minutes, accessory muscle use score at 30 minutes, 60 minutes and 180 minutes, and heart rate at 30 minutes, 60 minutes and 180 minutes.

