The outcomes which are measured at different time points will be averaged for each group and plotted to visualize the trajectory of those outcomes.

Differences in length of stay (hours) in the ER and the total doses of albuterol and ipratropium will be compared using T-tests or non-parametric methods (e.g., Mann-Whitney test) as depending on the distribution of the data. The proportion of patients in each group who require hospitalization will be compared using a Chi-square test.

C. Subject Characteristics

1. Subject criteria:

The study will be conducted at the emergency department at Tufts Medical Center.

a) Inclusion criteria:

- Acute asthma exacerbations presenting to the emergency room
- Peak expiratory flow rate at presentation <50%40% of predicted
- Enrolment within 90 minutes of the arrival to the ER
- Age 18-55 years old

b) Exclusion criteria:

- History of chronic obstructive pulmonary disease
- Clinical evidence to suggest a non-asthmatic cause of bronchospasm as determined by the treating physician
- Clinical evidence of acute coronary syndrome
- Respiratory failure requiring mechanical ventilation either invasive or non-invasive
- Tachyarrhythmia other than sinus
- Agitated or uncooperative
- Inability to provide informed consent

c) Withdrawal/Termination criteria:

The subject will be withdrawn from the study if any of the following:

- The subject develops respiratory failure requiring mechanical ventilation (invasive or non-invasive)
- The subject becomes unable to perform peak flow measurement at the pre-specified time points
- The treating physician determines that it is not clinically advisable to continue with the study.
- The subject opts to decline to sign the second part of the informed consent form. In this case, the data collected may not be used for the study.

A study participant will have the right to withdraw from the study at any point of the study.

A study participant may not participate in another research study while participating in this study.

D. Risk/benefit assessment:

1. Physical risk:

Patients in both the intervention and control arms are at risk for developing respiratory failure as a result of severe asthma exacerbation and it is unknown if the risk of such complications is higher in any arm. It is possible that the Aeroneb group patient may experience more frequent side effects related to potentially more albuterol and ipratropium delivery and those side effects may include tremor and arrhythmias.

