In order to blind the treating physician and the recording investigator, a sign "treatment in progress" will be displayed at the outdoor of the ER room when the patient is getting the bronchodilator treatment. The nebulizer devices will be placed in the box between the bronchodilator treatment sessions. The physician and the recording investigator will be asked if possible to see the patients only when the sign is taken off the outdoor.

-Once assigned, all the bronchodilator treatments in the ER will be administered using the nebulizer device assigned to that patient.

-The Peak flow and FEV1 will be measured using Spirometer (micro I). Both values will be obtained through the same exhalation maneuver.

-Patient will be treated and managed according to the asthma ER adult protocol or as directed by the ER physician who is in charge of patient's care

-After the study procedures have been performed and the subject is determined to be in stable condition and have the capacity to make medical decisions, the investigator will approach the subject again and review all the elements of the ICF again with the subject. The collected data will be used only if the subject signs both parts of the informed consent.

-Within two weeks of the subject participation, the research team will attempt to conduct a phone interview with the subject to obtain their feedback on the study procedures and mainly on the informed consent process. The phone interview questionnaire is included in the supplement

-The research team will report to the IRB the progress of the study including the consent process after enrolling the first 10 patients.

3. Subject Timeline:

During the study several data will be recorded, most of them are standard hospital recording, which are conducted frequently. These data will be collected at baseline and at multiple points after the initial bronchodilator therapy (at 30 ± 10 minutes, 60 ± 10 minutes, at 180 ± 10 minutes and upon disposition from the ER). All recorded data are obtained through noninvasive measurements. No samples of any body component will be taken that is not part of the normal standard hospital protocols.

The results that will be collected are summarized in table 1.

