We do not anticipate serious complications attributable to the device, but will monitor patients for potential adverse effects such as discomfort or cough. Any serious adverse events that occur during use are more likely due to the underlying disease than the device itself, but will be reported promptly to the IRB by the investigators per the reporting timeframes described above.

The Research team will report to the IRB the process of the informed consent after enrolling 10 patients (if this occurs before the study continuing review).

G. Subject Participation

1. Recruitment:

Patients presenting with severe asthma exacerbation to Tufts Emergency Room will be recruited on to the study. Patients who meet any exclusion criteria will not be screened for possible enrollment. Patients will be approached at their bedside by the PI, co-investigator or research coordinator. No advertisements will be used.

2. Registration:

Patients, that can potentially take part in the study, will be assessed by the PI or the co-investigator for their ability to fulfill the eligibility criteria and meet the exclusion criteria, as listed above.

3. Screening Interview/questionnaire: Not applicable

4. Transportation: Not applicable

5. Informed consent process and timing of obtaining of consent:

The participant must have the full mental capacity to provide the consent. The consenting process will be two steps process, each step will involve face-to-face meeting with one of the study investigators at bedside in the ER room

1-The first part of the consent will cover all the essential elements of the informed consent. Given the acuity of the medical condition, it is anticipated that the total amount of time given to this step of the informed consent will be no longer than 10 minutes. No study related procedures will be conducted until this step of the informed consent is signed off by the subject. Permission will also be obtained from the primary provider for the participation of the patient in the study before a discussion with the patient regarding consent occurs.

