The patient will be provided with a copy of the consent form to read and all questions will be answered prior to their signing the first part of the consent. In order to determine the subject's understanding of the study, the subject will be asked to describe his understanding of the study back to the investigator obtaining the consent. The subject will be encouraged to call the investigator with any questions. No study procedures will be performed other than chart review to determine eligibility prior to obtaining informed consent. The investigators recognize the potential vulnerability of the patient in this setting (i.e., being acutely ill) and thus will terminate the consent discussion in any situation where the patient appears to be uncomfortable or apprehensive about providing consent for participation in the study.

2-The second part of the informed consent will take place after the study procedures have been performed and the patient condition has been stabilized. The investigator will meet face-to-face with the subject and review the ICF again with the subject in more detailed manner. The subject will be asked to sign a separate section of the ICF re-consenting that they agreed to participate in the study.

Subjects who do not sign the second part of the ICF will be withdrawn from the study and data collected on those subjects may not be used for the study.

It will be explained that if they refuse to be in the study it will not affect their care or medical treatment outside of the study.

If non-English speaking persons will be enrolled, state the informed consent process for enrolling the subjects, including who will conduct the consent interview, use of interpreters, translated documents, etc.: Only English speaking persons will be enrolled as it will be difficult to communicate with non-English speaking patients about the PEFR maneuvers and the dyspnea scoring. Timely assistance from the interpreter service personnel may not be feasible given the acuity of the cases. Interpreter phone will not be sufficient as it would be hard to demonstrate the maneuver through phone interpretation.

6. Location where study will be performed:

The study will be performed at the Emergency Room at Tufts Medical Centre. Study records will be kept in a locked filing room.

7. Personnel who will conduct the study, including:

a. Present during study procedure(s) and their proximity during the study:

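### The analysis set labelled ITT is restricted to patients who completed the study procedures and both consent parts, and this restriction is not reconciled with the withdrawal rules

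*Combined protocol and SAP*

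**What the plan says.** **Analysis set.** Section III.B states that treatment evaluations follow the ITT principle, "using the data collected from all randomized participants who completed the study procedures including the two parts of the informed consent form". No section defines completion of the study procedures. It cannot mean every scheduled measurement, because III.E.3.2 waives the 3-hour data for patients discharged within 3 hours. No method for missing data and no sensitivity analysis is given.

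**Withdrawal.** Section III.C.1.c has four triggers: respiratory failure needing invasive or non-invasive ventilation; loss of the primary measurement ("The subject becomes unable to perform peak flow measurement at the pre-specified time points"); a decision by the treating physician; and consent ("The subject opts to decline to sign the second part of the informed consent form"). Only the consent trigger carries a statement that the data may not be used.

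**Consent.** Section III.E.2 says: "The collected data will be used only if the subject signs both parts of the informed consent". Section III.G.5 sets the timing: "The second part of the informed consent will take place after the study procedures have been performed and the patient condition has been stabilized". It also sets the place: "each step will involve face-to-face meeting with one of the study investigators at bedside in the ER room".

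**Items recorded at disposition.** Table 1 and III.E.3.3 include intubation, need for NIV, disposition and length of stay.

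**Numbers.** Section III.B plans 34 per group, and expects to enrol around 110 so that 68 complete the study objectives.

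**The concern.** A set that depends on completion after randomisation is not an ITT set, and two of the withdrawal triggers follow the disease outcome directly. A patient who is ventilated, or who can no longer perform peak flow, is likely to be among the worst responders. If such patients leave the analysis, randomisation no longer protects the comparison. This applies to PEFR, and also to hospitalisation and length of stay, which could be known for these patients without a peak flow reading.

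Consent is a second filter. Part two is sought after the procedures and once the patient is stable, so a patient who deteriorates may never be asked and is lost without refusing. The patient is not blinded and decides after experiencing the treatment.

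Because completion is undefined, two analysts could build different primary sets from the same data. One might require only the 30-minute reading and both signatures, another every unwaived reading. The choice could be made after the data are seen, and either result would be reported as ITT.

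**Working it through.** **1. The plan's own figure.** Inputs from III.B: difference 10.0, SD 14.4, two-sided alpha 0.05, equal-variance t-test, 34 per group. SE = 14.4 × √(2/34) = 3.49. With 66 df, the noncentral t gives power 80.5% at 34 per group and 79.3% at 33. The stated 34 reproduces, so the sample-size arithmetic is not in question.

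**2. What is known about losses.** 110 − 68 = 42, and 42/110 = 38.2%. This mixes screen failures, disqualification and drop-out, so it is only a ceiling. All loss rates and correlations below are assumptions.

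**3. Shift in the primary difference.** Suppose a fraction p of an arm is lost from the severe end, and severity has correlation ρ with the 30-minute PEFR. The retained mean rises by ρ × 14.4 × φ(z_p)/(1 − p). The factor φ(z_p)/(1 − p) is 0.1086 at 5%, 0.1950 at 10%, 0.2743 at 15% and 0.3500 at 20%.

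For 5% Aeroneb and 15% jet the factor difference is 0.1086 − 0.2743 = −0.1657. At ρ = 0.3 the shift is 0.3 × 14.4 × (−0.1657) = −0.72.

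| Loss, Aeroneb v jet | ρ = 0.3 | ρ = 0.5 | ρ = 1.0 (bound) |
|---|---|---|---|
| 5% v 10% | −0.37 | −0.62 | −1.24 |
| 5% v 15% | −0.72 | −1.19 | −2.39 |
| 5% v 20% | −1.04 | −1.74 | −3.48 |
| 10% v 10% | 0 | 0 | 0 |

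Reversing the loss rates reverses the sign. After baseline adjustment the shift is (ρ − r·g) × 14.4 × (factor difference), where r is the baseline-outcome correlation and g the severity-baseline correlation. For 5% v 15%, with r of 0.3 or 0.5 and g from 0 to 0.3, it lies between −0.36 and −1.19.

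**4. Type I error and power of the planned ANCOVA (5% v 15%, 34 analysed per arm, g = 0).** With no loss, the SE is 14.4 × √(1 − r²) × √(2/34): 3.02 at r = 0.5 and 3.33 at r = 0.3. Power at a true 10 points is then 90.3% and 84.1%. Selection also shrinks the variance, so power after loss was simulated (40,000 trials).

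| r | No loss (formula) | ρ = 0.3 | ρ = 0.5 | Fall |
|---|---|---|---|---|
| 0.5 | 90.3% | 86.2% | 84.3% | 4.1 and 6.0 |
| 0.3 | 84.1% | 78.6% | 76.6% | 5.5 and 7.5 |

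Simulated type I error is 0.056 to 0.067. The documents do not give r.

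**5. Hospitalisation.** With a common true rate q, and a share k of lost patients admitted, the retained rate is (q − k·p)/(1 − p). For losses of 5% v 15% and k = 1:

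- q = 20%: 15.8% v 5.9%, gap 9.9 points
- q = 33%: 29.5% v 21.2%, gap 8.3
- q = 50%: 47.4% v 41.2%, gap 6.2
- q = 60%: 57.9% v 52.9%, gap 5.0

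The 20% to 33% is the general ED figure in the Background. The 50% to 60% is an assumption for a more severe population. With k = 0.5 the first two gaps fall to 3.7 and 2.1.

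**The case against.** **Withdrawn patients may be meant to stay in.** Section III.C.1.c attaches loss of data to the consent trigger alone, which suggests that data from the other three withdrawals remain usable. Intubation and NIV are recorded at disposition, which would make little sense if recording stopped at ventilation. This stands, and it limits the claim. A reader might infer that the plan definitely discards every ventilated patient; the documents do not say so. The restriction in III.B is still there, so the sections conflict.

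**The consent sections look inconsistent.** III.C.1.c withdraws a patient who opts to decline part two, while III.G.5 says: "Subjects who do not sign the second part of the ICF will be withdrawn from the study". A reader might see a further ambiguity about who is analysed. There is none, because III.E.2 bars the data in either case. This exclusion is an ethics condition, not a statistical choice.

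**Blinding and sample size.** The treating physician is blinded where possible, which limits arm-dependent physician withdrawal. It does not affect withdrawals that follow the outcome itself. Enrolling about 110 to obtain 68 restores numbers, not comparability.

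**The bias may be small or absent.** A threefold imbalance in losses has no support in the documents. Even so, the shift is about a tenth of the planned difference, and equal losses give none. This stands, and it bears on how serious the point is.

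**Conclusion.** The contradiction is certain: the plan names ITT and then restricts the set to undefined completers, and III.B and III.C.1.c do not agree on patients withdrawn for reasons other than consent. Followed literally, III.B makes outcome-related exclusions in the PEFR, hospitalisation and length-of-stay comparisons.

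The size and direction of the bias are not known. Under the assumed 5% v 15% the shift is 0.7 to 1.2 points before baseline adjustment, against a planned 10. The false hospitalisation gap is at most 8 to 10 points at a true rate of 20% to 33%, about 5 to 6 at an assumed 50% to 60%, and smaller if some lost patients were not admitted.

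A reader might infer that the set favours Aeroneb, or that the trial cannot give a valid answer. Neither follows. More severe losses from jet would work against Aeroneb, the reverse would favour it, and losses equal in rate and in relation to outcome would do neither. On the size of the bias, this is a point that should be fixed rather than one that invalidates the design.

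**What to change.** - **III.B, primary set.** Define it as all randomised patients, analysed as randomised, whose data may be used under the consent rule in III.E.2. Rename the present set completers, define it, and use it as a sensitivity analysis.
- **III.C.1.c.** Leave the triggers unchanged. State that withdrawal for reasons other than consent does not remove data already collected or the Table 1 disposition items, unless the patient withdraws permission for data use.
- **Missing 30-minute PEFR.** Fix the handling in advance, for example multiple imputation from arm, baseline and later PEFR feeding the ANCOVA, with one sensitivity analysis using a pre-set unfavourable value.
- **Reporting.** Tabulate exclusions by arm and reason, separating refusal of part two from inability to sign it.
- **Limitation.** State that patients who do not sign part two stay outside the set. If half of the assumed losses were of this kind and the most severe (2.5% v 7.5%), 0.4 to 0.7 of the 0.7 to 1.2 points would remain. Any change to when or where part two is offered is a separate question for the IRB.
- **Sample size.** State whether the 68 counts patients with a 30-minute PEFR or the wider set.

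The cost is wording in two sections, one table, a small amount of extra analysis, and slightly wider intervals from imputation. The disposition items are already collected.

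### Hospitalisation, length of stay and drug totals get valid but unadjusted tests; prespecifying adjustment for baseline PEFR would cost almost nothing and could add modest precision

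*Combined protocol and SAP*

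**What the plan says.** All the analysis rules are in protocol section III.B (Sample size and statistical analysis(es)).

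- **Primary outcome**, PEFR % predicted at 30 minutes: "analysis of covariance (ANCOVA) with adjustment for baseline PEFR will be utilized".
- **Timed secondary outcomes** (PEFR, FEV1, Borg score, accessory muscle score, heart rate): ANCOVA adjusted for baseline values, with repeated measures where appropriate.
- **Length of stay and drug totals**: length of stay and "total doses of albuterol and ipratropium will be compared using T-tests or non-parametric methods", the choice depending on how the data are distributed.
- **Hospitalisation**: "The proportion of patients in each group who require hospitalization will be compared using a Chi-square test".
- **Level**: "All statistical testing will be two-sided with alpha=0.05".

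No adjusted or sensitivity analysis is given for the last four outcomes (hospitalisation, length of stay, albuterol total, ipratropium total). Baseline PEFR is recorded at enrolment (section III.E.3.1 and Table 1). Randomisation is 1:1 in permuted blocks of 6, with no stratification by PEFR stated (section III.B).

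**The concern.** The protocol uses PEFR as its measure of severity, and its rationale names a shorter emergency stay and fewer admissions as the expected benefits. For those outcomes, neither the randomisation as described nor the analysis takes account of how severe each arm was at entry. With 34 patients per arm, chance differences in severity can be noticeable. If baseline PEFR predicts admission, stay or drug use, a comparison that ignores it gives up some power and is harder to interpret when the arms happen to differ. The covariate is already collected. It should be close to complete, because eligibility itself depends on PEFR.

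**Working it through.** **1. The plan's own figure.** The plan states "Group sample sizes of 34 and 34 is required to achieve a power" above 80% when "the groups mean difference is 10.0" points, "with a standard deviation for both groups of 14.4", at a "significance level (alpha) of 0.050 using a two-sided two-sample equal-variance t-test". The noncentrality is 10/(14.4 × √(2/34)) = 10/3.49 = 2.86. Exact power is 79.3% at 33 per arm and 80.5% at 34, so 34 reproduces. It concerns the primary outcome only. No power is given for the four outcomes here.

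**2. Chance imbalance in baseline PEFR at 34 per arm.** The standard error of the difference in means is √(2/34) = 0.243 SD, so the 95% range is ±1.96 × 0.243 = ±0.48 SD. The probability of a difference beyond 0.25 SD in either direction is 30%, and beyond 0.5 SD it is 4%.

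**3. Length of stay and drug totals.** The documents give no correlation ρ between baseline PEFR and these outcomes, so ρ is assumed over a range. Adjustment multiplies the variance by 1 − ρ², and 68 adjusted patients are worth 68/(1 − ρ²) unadjusted ones. For rank ANCOVA, read ρ as a rank correlation; the figures are then approximate.

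| ρ (assumed) | variance reduction | equivalent patients | power for a 0.5 SD difference |
|---|---|---|---|
| 0 | 0% | 68 | 52.9% |
| 0.1 | 1% | 68.7 | 53.2% |
| 0.2 | 4% | 70.8 | 54.5% |
| 0.3 | 9% | 74.7 | 56.7% |
| 0.4 | 16% | 81.0 | 60.1% |
| 0.5 | 25% | 90.7 | 65.0% |

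If the arms differ by 0.48 SD at baseline, the unadjusted difference shifts by 0.48ρ: 0.05, 0.14 and 0.24 SD at ρ = 0.1, 0.3 and 0.5. In z units the shift is 1.96ρ with residual SD √(1 − ρ²), so the false-positive rate given that imbalance is about 5.3%, 7.9% and 12.9%. Averaged over all randomisations it stays at 5%.

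**4. Hospitalisation.** The introduction gives admission as about one-fifth to one-third; 33% is taken as the control rate. Assumed: a treatment odds ratio of 0.25 given baseline, and a fall in log-odds of admission per SD of baseline PEFR (the slope) from 0 to 1.4. Simulation used 34 per arm and 20,000 trials per setting. It compared the chi-square test with the likelihood-ratio test from a logistic model on arm and baseline PEFR.

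| slope per SD | chi-square power | adjusted power | gain (points) |
|---|---|---|---|
| 0 | 63.1% | 63.3% | 0.3 |
| 0.2 | 62.5% | 63.3% | 0.8 |
| 0.4 | 60.8% | 62.3% | 1.5 |
| 0.7 | 57.4% | 60.6% | 3.3 |
| 1.0 | 52.7% | 58.8% | 6.2 |
| 1.4 | 45.0% | 55.2% | 10.2 |

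(Gains were taken before rounding.) With no treatment effect, both tests rejected in 5.3% to 5.8% of trials at a 33% rate. At a 20% rate the chi-square rejected in 5.0% to 5.6% and the adjusted test in 5.5% to 6.1%.

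A 0.48 SD imbalance alone shifts admission by about 2 and 4 points at slopes 0.2 and 0.4, and by 7, 9 and 11 points at 0.7, 1.0 and 1.4. The standard error of the crude difference is √(2 × 0.333 × 0.667/34) = 0.114, or 11 points.

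**5. Events available.** With no effect, 0.20 × 68 ≈ 14 to 0.33 × 68 ≈ 22. With an odds ratio of 0.25, a 20% control rate becomes about 5.9%, giving 34 × (0.20 + 0.059) ≈ 9 events. At 33% the total is about 15 to 16. The model has two terms besides the intercept.

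**6. Power that remains.** Chi-square power for hospitalisation is about 21% for 20% against 10%, and 35% for 33.3% against 16.7%.

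**The case against.** A reader might infer more than the documents support, in four ways.

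- **That the plan contradicts itself.** It does not. The timed outcomes appear to be adjusted for their own baseline values, and admission, stay and drug totals have none. Using PEFR as a prognostic covariate is a separate choice.
- **That the simple tests are biased or inflate the error rate.** Under randomisation they hold their level. The imbalance matters only conditionally, and an 11-point shift, which needs both the 95% limit of imbalance and the steepest slope, is about one standard error of the crude difference. Baseline characteristics will also be summarised by arm, so an imbalance would be visible.
- **That precision is certainly being lost.** The background section links outcome to the 30-minute improvement in PEFR, not to its baseline value. Eligibility restricts baseline PEFR to a narrow range (the text shows both 40% and 50% of predicted as the limit). Treatment may precede enrolment, and length of stay starts at arrival, up to 90 minutes before randomisation. Each may weaken the association.
- **That adjustment would make hospitalisation well powered.** It would not.

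A further fair point is that 9 to 22 events is few for a logistic model, and at a 20% rate part of the apparent gain is slight anti-conservatism of the likelihood-ratio test.

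All of this stands, and it limits the point to an efficiency improvement. It does not remove it. The prognostic strength need not be known to justify adjusting, because the cost at zero association is negligible.

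**Conclusion.** The point holds as a cheap improvement to four secondary outcomes. They are tested validly but without a covariate that is already recorded. At a 33% control rate and an odds ratio of 0.25, adjustment adds about 0 to 2 points of power for hospitalisation at slopes up to 0.4 per SD, and about 3 to 10 points at slopes of 0.7 to 1.4. For length of stay and drug totals it removes 1% to 4% of the variance at correlations of 0.1 to 0.2, and 9% to 25% at 0.3 to 0.5. The slopes, correlations and treatment effect are assumptions; the documents supply none of them, so no single figure can be defended. The overall type I error of the planned tests, the primary analysis and the 34 per arm are not in question.

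**What to change.** Before unblinded data are seen, add to section III.B a single prespecified analysis adjusted for baseline PEFR % predicted for each of the four outcomes.

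- **Hospitalisation:** logistic regression on arm and baseline PEFR, reported as a standardised risk difference with 95% CI. Keep the chi-square test as the unadjusted check. The standardised risk difference avoids presenting a conditional odds ratio as if it were the crude effect.
- **Length of stay, albuterol total, ipratropium total:** rank ANCOVA on arm and baseline PEFR, as the one named method. It tolerates zero doses, which a log scale would not, and it removes the choice between t-test and Mann-Whitney after the data are seen.

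The cost is a few sentences and a few lines of code, with no new data. There are two small downsides. With about 9 to 22 events the likelihood-ratio test may run slightly above its level (about 5% to 7% at a 20% admission rate). Rank ANCOVA gives a test and not an effect in hours or dose units, so arm medians should be reported beside it. Hospitalisation should still be described as underpowered.

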3.2 During the study
The following variables (respiratory rate, heart rate, BP, O₂ sat, FIO₂, Dyspnea Borg score, cough, respiratory accessory muscle, peak flow and FEV1) will be recorded at the following time points after initial bronchodilator therapy (30±10 minutes, 60±10 minutes, 180±10 minutes and at the disposition from the ER). If the patient is discharged from the ER within 3 hours from the initial bronchodilator therapy then the data collection at 3 hours mark will be waived.

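### A patient who becomes unable to blow is withdrawn from the study, and the completers-only analysis can then drop that patient from outcomes that need no spirometry

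*Combined protocol and SAP*

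**What the plan says.** Three rules bear on a patient with no spirometry reading at a scheduled time.

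- **Withdrawal (III.C.1.c).** The list opens "The subject will be withdrawn from the study if any of the following" and includes "The subject becomes unable to perform peak flow measurement at the pre-specified time points". The withdrawal is from the study, not from one visit or one measurement.
- **Waiver (III.E.3.2).** For a patient "discharged from the ER within 3 hours from the initial bronchodilator therapy then the data collection at 3 hours mark will be waived". That patient otherwise stays in.
- **Analysis set (III.B).** The intention-to-treat evaluation uses "data collected from all randomized participants who completed the study procedures including the two parts of the informed consent form".

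Several secondary outcomes need no blow. The ANCOVA list in III.B includes "Borg dyspnea score at 30 minutes, 60 minutes and 180 minutes, accessory muscle use score at 30 minutes, 60 minutes and 180 minutes", and also heart rate at the same times. For hospitalization, "The proportion of patients in each group who require hospitalization will be compared using a Chi-square test". For the remaining ones, "Differences in length of stay (hours) in the ER and the total doses of albuterol and ipratropium will be compared" by t-test or a non-parametric test.

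**The concern.** Two patients without a 180-minute reading are handled in opposite ways. The one who went home early keeps a place in the study. The one who could not blow is withdrawn and, as a non-completer, can fall outside the analysis set.

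Everyone enrolled had a measured peak flow at entry, so becoming unable to blow later plausibly marks a poor response. The documents do not say this; it is an inference. If it is right, the patients removed tend to be those with high dyspnea scores and a high chance of admission. The Outcomes section (III.I) expects a PEFR gain to carry over to dyspnea, accessory muscle use, ER stay and hospitalization, so the loss falls on the outcomes meant to show that benefit. A patient with a valid 30-minute PEFR who is withdrawn at a later time may lose the primary value as well.

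**Working it through.** **1. The plan's own figure.** III.B gives a difference of 10, SD 14.4, two-sided alpha 0.05 and a two-sample t-test. The noncentral t calculation gives n = 33.54, so 34 per arm, with power 80.5% at 34. The stated 34 and 34 reproduces and is not in dispute.

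**2. Withdrawal rate.** III.B anticipates about 110 enrolled for 68 completers, a loss of 42/110 = 38.2%. This pools screen failures, disqualifications and drop-outs. No rate of withdrawal for inability to blow is given, so everything below rests on assumed rates.

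**3. One arm, k patients withdrawn.** Assumed inputs: 34 patients, Borg 9 in each withdrawn patient against a mean of 5 in the rest, 11 true admissions, and every withdrawn patient admitted.

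- True Borg mean = ((34 − k)×5 + k×9)/34; recorded mean = 5.0.
- True admission = 11/34; recorded admission = (11 − k)/(34 − k).

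| k | True Borg | Recorded Borg | True admission | Recorded admission | Shift (points) |
|---|---|---|---|---|---|
| 1 | 174/34 = 5.12 | 5.0 | 32.4% | 10/33 = 30.3% | 2.0 |
| 2 | 178/34 = 5.24 | 5.0 | 32.4% | 9/32 = 28.1% | 4.2 |
| 3 | 182/34 = 5.35 | 5.0 | 32.4% | 8/31 = 25.8% | 6.5 |

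Shifts come from unrounded fractions; subtracting the rounded percentages in the last row gives 6.6.

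**4. Between arms, same counts.** Let both arms truly have 11/34 admitted.

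- 1 withdrawn in one arm and 3 in the other: 30.3% against 25.8%, a false difference of 4.5 points favouring the arm that lost more.
- 3 withdrawn in each: 25.8% in both, no false difference, but both rates too low.

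**5. Between arms, by rate.** Section I puts poor response with admission at about one-fifth to one-third. Assume the same true rate p in both arms, a fraction w withdrawn, and all of those admitted. Recorded rate = (p − w)/(1 − w).

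| Withdrawn, Aeroneb / jet | True p | Recorded, Aeroneb / jet | False difference (points) |
|---|---|---|---|
| 5% / 5% | 20% | 15.8% / 15.8% | 0 |
| 5% / 10% | 20% | 15.8% / 11.1% | 4.7 |
| 5% / 10% | 33.3% | 29.8% / 25.9% | 3.9 |
| 5% / 15% | 20% | 15.8% / 5.9% | 9.9 |
| 5% / 15% | 33.3% | 29.8% / 21.6% | 8.3 |

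Of 34 patients, 5%, 10% and 15% are 1.7, 3.4 and 5.1, so the higher rates go beyond the range in step 3.

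**6. Primary outcome, outer bound.** This applies only if valid 30-minute values are discarded on later withdrawal. Assume normal values with SD 14.4, and that the lowest fraction w is lost. The unadjusted mean rises by 14.4×φ(z)/(1 − w), where z is the w-quantile: 1.56, 2.81 and 3.95 points for 5%, 10% and 15%. A true difference of 10 becomes 8.8 with 5% lost on Aeroneb and 10% on jet, or 10 + 1.56 − 3.95 = 7.6 with 5% and 15%. It stays at 10.0 with 10% in each.

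**The case against.** The strongest reply is that the documents never say recording stops at withdrawal. A reader might infer that withdrawal ends all collection, but the text does not support that. Data use is expressly restricted only for refusal of the second part of the consent. Table 1 and section III.E.3.3 record intubation and non-invasive ventilation at disposition, although ventilation is itself a withdrawal criterion, so some recording afterwards may be intended. Hospitalization, length of stay and drug totals belong to the same disposition block. This stands: collection after withdrawal is unspecified, not prohibited. It does not remove the problem, because the completers-only wording in III.B can still exclude data that were recorded.

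Three further readings are tempting and go too far.

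- *One missed reading at 60 or 180 minutes means withdrawal.* The criterion speaks of time points in the plural and does not say whether one failure is enough.
- *A patient moved to the floor or ICU before 180 minutes falls under the withdrawal rule.* Leaving the ER is not inability to blow. What can be said is that the waiver speaks of discharge while III.E.3.3 speaks of disposition to home, floor or ICU, so its scope is unclear for admitted patients.
- *The rule biases against the more effective device.* That needs unequal losses between arms and poor response among those lost. The documents establish neither.

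Also, a patient who cannot blow at 30 minutes has no primary value under any rule. The main exposure is therefore in the secondary outcomes.

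**Conclusion.** The point holds as a gap and an inconsistency in the plan. Sections III.B, III.C.1.c and III.E.3.2, followed literally, can drop patients who become unable to blow from six kinds of outcome that need no blow, and possibly discard a valid 30-minute PEFR. If such losses differ between arms, the arm with more of them looks better than it is. Equal losses need not create a between-arm difference, but they still make both arms look better.

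With 1 to 3 withdrawn in one arm, the understatement is about 0.12 to 0.35 Borg units and 2 to 6.5 percentage points of admission. This assumes Borg 9 against 5 and that every withdrawn patient is admitted. The size and direction of any between-arm bias cannot be determined from the documents. The matter should be corrected; it does not undermine the sample size.

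**What to change.** 1. **III.C.1.c:** separate a missed spirometry reading from loss of study data. Record the reading as not done, with the reason. Keep all earlier readings. Continue the non-spirometry measures while the patient is in the ER, and collect disposition data, subject to the two-part consent.
2. **III.B:** replace the restriction to those who completed the study procedures, so that all randomized patients with both consents are analysed with the data they have. Report missing spirometry by reason and arm. Without this change, a patient retained under item 1 could still be excluded as a non-completer.
3. **III.E.3.2:** word the 3-hour waiver to cover leaving the ER for any destination (home, floor or ICU).
4. **Reconcile** III.B, III.C.1.c, III.E.2, III.E.3.2, III.E.3.3 and Table 1 on what withdrawal means, including whether one missed reading triggers it. III.E.2 ties all ER bronchodilator treatments to the assigned device. Whether that continues after withdrawal is a clinical matter that this fix does not decide.

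The cost is protocol wording and one reason code on the form. The sample size is unchanged. The downside is that some spirometry values will be explicitly missing; the fix cannot supply a 30-minute PEFR that was never obtained.
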